APPENDIX 1. EAGLE 2 Case Report Form

| Local Patient Identifier | not uploaded to REDCap | Unique REDCap Identifier | |
|---|---|--------------------------|--|
| Pre-operative data | | | |
| Age (on day of operation) | Years | | |
| Sex | Male / Female | | |
| American Society of Anaesthesiologists (ASA) grade | 1 / 2 / 3/ 4/ 5 | | |
| Previous abdominal surgery | No / Yes | | |
| History of ischemic heart disease or cerebrovascular disease | No / Yes | | |
| History of diabetes mellitus | No / Yes | | |
| Body Mass Index >30 | No / Yes | | |
| Oral anti-coagulants | No / Yes | | |
| Pre-operative total protein level (g/dL) – nearest 0.5 units | | | |
| Pre-operative haemoglobin (g/dL) | | | |
| Procedure indication | Malignancy / Inflammatory bowel disease / Other | | |
| Intra-operative data | | | |
| Bowel preparation | None / Mechanical bowel preparation only / Mechanical bowel preparation with oral antibiotics | | |
| Primary operating surgeon | Consultant colorectal surgeon / Trainee colorectal surgeon / Consultant general surgeon / Trainee general surgeon | | |
| Most senior surgeon in theatre | Consultant colorectal surgeon / Trainee colorectal surgeon / Consultant general surgeon / Trainee general surgeon | | |
| Procedure urgency | Elective (planned) / Expedited (within two weeks of decision to operate) / Emergency (unplanned) | | |
| Operative approach | Open, Laparoscopic (completion, conversion to open), Robotic (completion, conversion to open) | | |
| Operative field contamination | Clean-contaminated / Contaminated / Dirty | | |
| Anastomosis formed | Stapled / Handsewn / No anastomosis (end ileostomy formation) | | |
| If yes: Anastomotic configuration | Side-to-side / end-to-side / end-to-end | | |
| If yes: Is there a defunctioning loop ileostomy | No / Yes | | |

| | |
|---|--|
| If yes: Was the anastomosis tested? | No / Yes -air leak test / Yes - probed with forceps |
| If yes: Did the anastomosis require revision? | No / Yes |
| Intra-operative complications | Blood loss >1L / Operating time >4h / Solid organ or ureteric injury / Vascular injury / Blood transfusion / Hemodynamic instability / Vasopressor requirement (select all that apply) |
| Duration of surgery (minutes) knife-to-skin to completion of skin closure | 1-60 / 61-119/ 120-179/ 180-239/ ≥240 |
| Was an ESCP Safe-anastomosis Checklist completed? | Yes / No |
| Was anastomotic leak risk calculated pre-operatively ? | Yes / No |
| Was anastomotic leak risk calculated intra-operatively ? | Yes / No |
| Has the senior surgeon completed the Safe-anastomosis module? | Yes / No |
| Post-operative data | |
| Post-operative critical care admission | None / Planned from theatre / Unplanned from theatre / Unplanned from ward |
| Total length of hospital stay | Days (up to 30 post-operative days) |
| Anastomotic leak or intra-abdominal/pelvic collection | None / Grade A – requiring no further intervention, radiologically diagnosed / Grade B – requiring radiological reintervention / Grade C – requiring surgical reintervention |
| If yes: How was the leak diagnosed? | Clinical diagnosis only/ Ultrasound imaging/ CT imaging/ MR imaging/ Intra-operative diagnosis |
| Re-operation within 30 days | No / Yes |
| Re-admission within 30 days | No / Yes |
| Mortality within 30 days | No / Yes |

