| | Short-term Complications / reinterventions | | | ✓ |

Training platform

The training platform for the audit is the ESCP Safe-anastomosis Online Educational Module. This is an Electronic Learning Management System which houses a five-modular educational platform, freely accessible at <https://eagle-escp.eu.com/>. The modules are:

1. **Decision making**, including a pre-operative risk stratification tool for anastomotic leak
2. **ESCP Safe-anastomosis checklist**, including components and implementation within a theatre team
3. **Preparing for anastomosis**, including anastomotic healing bowel preparation, choice of stapled versus handsewn anastomoses
4. **Stapled anastomosis**, including harmonising technique and checking for technical failure.
5. **Handsewn anastomosis**, including harmonising technique, common variations and checking for technical failure.

It is intended that this educational module should be completed by any providers of colorectal surgical procedures (including consultant/attending surgeons, trainee/resident surgeons, and surgical care practitioners/allied healthcare professionals in surgery) prior to participation in the audit.

Validation of learning platform

The training program has been reviewed by the ESCP Education Committee and revised. It has also been reviewed by the independent Study Steering Committee. More than 2500 surgeons completed the online training during delivery of the EAGLE 1 study.

Data collection and follow-up

Data will be collected in two phases. During the index admission pre-operative and intra-operative data will be collected. Local Principal Investigators will establish pathways in their hospitals to ensure robust data collection; for example, pre-operative data could be collected on the morning prior to surgery, with intra-operative data fields completed in theatre immediately following completion of the procedure. Alternatively, all data could be collected in theatre, or in the post-operative ward.

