Planned additional analyses

Pre-planned exploratory sub-group analyses of the primary outcome will be performed in the following groups:

- *At cluster (hospital) level:*
- Number of beds (<500 versus ≥500 total hospital beds).
- Right colectomy volume (<10 patients versus ≥10 patients per 2 month period).
- Early adoption (early versus late study entrants).
- Health service expenditure per capita in purchasing parity (top versus middle versus bottom tertile).
- Proportion of operating surgeons in each centre completing the online training modules prior to 'post-implementation' data collection (high [≥80%], intermediate [50-79%], low [<50%]).
- World Bank income group (high versus middle/low-income country).

At patient level:

- Indication for surgery (malignant versus benign, e.g. inflammatory bowel disease).
- Procedure urgency (elective versus expedited/ emergency).
- Age (≤65 years versus >65 years).
- Operative approach (open versus laparoscopic/ robotic).
- Anastomotic technique (stapled versus handsewn anastomosis).
- Primary operating surgeon experience as reported (trainee versus consultant).
- Primary operating surgeon specialism as reported (general versus colorectal surgeon).
- Reverse analysis will also be undertaken to explore what are the characteristics of hospitals with a big change versus no change, and do these differ in respect of cluster characteristics.

STUDY ORGANISATIONAL STRUCTURE

EAGLE 2 Audit Office

The coordinating centre for EAGLE 2 is based at the University of Birmingham in the Birmingham Centre for Observational and Prospective Studies (BiCOPS). Members of this group also represent the European Society of Coloproctology (ESCP) and sit on both the research committee and cohort studies committee of ESCP.

Local teams

We envisage that most hospitals opening for the audit will identify a team of up to 5 members, which may include surgical colleagues, trainee doctors, nurses, medical students, or others involved in the routine clinical care of eligible patients, depending on local circumstances. Members of this group will be responsible for the local conduct of the audit at their site, including helping to identify potential patients and record data onto the EAGLE 2 REDCap database.

Publication policy

The output from this research will be published under a single corporate authorship group: “European Society of Coloproctology (ESCP) collaborating group”.

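### The only training item on the CRF has no time reference, so training finished after an operation can be recorded as prior training and cannot be corrected later

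*Protocol*

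**What the plan says.** Three places in the protocol bear on when training must have happened.

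- **Training platform** sets the intention. The module is meant for everyone who provides colorectal surgery, to be completed "prior to participation in the audit".
- **Planned additional analyses** bands hospitals as high (80% or more), intermediate (50-79%) or low (under 50%) by the proportion of operating surgeons "completing the online training modules prior to" the data collection that it calls post-implementation.
- **Appendix 1 (CRF)** holds the only training field: "Has the senior surgeon completed the Safe-anastomosis module", answered Yes or No. It is the last item before the post-operative block.

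The secondary objective is to assess uptake and acceptability of the training platform. For the primary analysis, the section Statistical analysis plan treats patients in the second period as exposed, whether or not the training was put into practice.

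**The concern.** The two passages that define who counts as trained both require completion beforehand. The field that records training asks only whether it has been completed, which can be read as status when the form is filled in. The two leak-risk items just above it are tied to the pre-operative and intra-operative phases; this one is tied to nothing.

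If post-operative training enters as Yes, uptake at the time of surgery is overstated, and any comparison by training status mixes operations done before training into the trained group. That pulls an observed difference towards zero. A statistical analysis plan cannot repair this, because it cannot recover a date that was never collected.

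**Working it through.** The protocol gives no figure to reproduce here. The check is a comparison of passages, followed by arithmetic for scale only.

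**1. Can late training be recorded as Yes?** Under Patient identification, patients may be identified after surgery, up to discharge. Under Data collection and follow-up, pre-operative and intra-operative data belong to the index admission, and all of them may be collected on the post-operative ward. Under Data Management, a paper form may be transcribed later, and missing items are queried back to the site. An answer can thus be given after the operation, and the item does not direct the respondent back to the operation date. Prior training is stated as an intention, and nothing on the form verifies it for the individual surgeon.

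**2. Can it be corrected afterwards?** That would need the operation date, the surgeon's identity and the completion date. The printed CRF has age on the day of operation but no operation date. It records the primary operating surgeon and the most senior surgeon in theatre by grade and specialty only. No completion date is asked for. The training sits on a learning management system, which may hold dated records, but the protocol describes no extraction or linkage.

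**3. Which results depend on it?**

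| Result | Uses the training item? |
|---|---|
| Primary mixed-effects model | No; exposure is by period |
| Overall 30-day leak rate | No |
| Training-proportion subgroup (exploratory) | If the proportion is built from this item; the protocol names no source |
| Uptake, or leak rate by training status | Yes, if described from CRF data |

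**4. Scale for the subgroup bands.** Suppose the hospital proportion is built from these answers. With 5 operating surgeons, one wrong Yes moves a centre from 3/5 = 60% (intermediate) to 4/5 = 80% (high). With 10, it moves from 7/10 = 70% to 8/10 = 80%, again crossing the boundary. The numbers of surgeons are assumptions.

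**5. Scale for a Yes/No description.** Let m be the share of Yes records in which training came after the operation. Then

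observed rate in Yes = (1 − m) × trained rate + m × untrained rate,

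so the observed difference is (1 − m) times the true one. Take 8.1% as the untrained rate (Existing international data) and half of it, 4.05%, as the trained rate (the fall of almost 50% reported there for centres with 80% of the team trained):

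- m = 0.10: 0.9 × 4.05 + 0.1 × 8.1 = 4.46%; difference 0.9 × 4.05 = 3.65 points instead of 4.05.
- m = 0.30: 0.7 × 4.05 + 0.3 × 8.1 = 5.27%; difference 0.7 × 4.05 = 2.84 points.

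The values of m are assumptions without support in the protocol. The 4.05% applies a centre-level effect to individual surgeons, and no Yes/No contrast by senior surgeon is planned. This shows the mechanism; it is not an estimate of harm.

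**The case against.** The strongest reply is that training is a condition of entry: the audit is open to centres whose surgical team has already trained, so late training should be rare. The item sits among intra-operative data, collected during the index admission, and the subgroup definition already states the timing. The platform may also hold completion dates, and the derivation of the hospital proportion may be left to a statistical analysis plan. Much of this stands. It makes the problem smaller and confines it to secondary uses. It does not supply the missing time reference, and no passage describes a second source.

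A reader might infer more than the protocol supports:

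- **That partial training counts as trained.** The platform is "This is an Electronic Learning Management System which houses a five-modular educational platform", and its second part is the "ESCP Safe-anastomosis checklist", so the CRF wording could be taken to mean one part of five. But the section names the whole platform, in the singular, as the Safe-anastomosis Online Educational Module and says "It is intended that this educational module should be completed by any providers of colorectal surgical procedures". Use of the checklist has its own CRF item, and the training item asks about completion. The one-of-five reading is weak.
- **That an outdated EAGLE 1 course counts as trained.** The protocol says "The training program has been reviewed by the ESCP Education Committee and revised" and, separately, "More than 2500 surgeons completed the online training during delivery of the EAGLE 1 study". It does not say which came first. A revision before EAGLE 1 fits the text equally well.
- **That forms are routinely completed weeks after surgery.** This is not the process described for pre-operative and intra-operative data.

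**Conclusion.** The point holds in a limited form. The sole training field does not record the timing that Training platform and Planned additional analyses require, and the printed CRF offers no means of restoring it. Training finished between the operation and completion of the form can be recorded as Yes; no rule says that it must count as exposure.

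The effect is confined to the exploratory training-proportion subgroup, where it draws on this item, and to any account of uptake or leak rate by training status. It would be wrong to infer bias in the primary analysis, which as written assigns exposure by period. The size is unknown: it depends on how many surgeons train during the window and how late forms are completed, and the protocol gives neither. The case for acting is that the correction is nearly free before data entry and unavailable afterwards.

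**What to change.** Reword the CRF item to: *Had the senior surgeon completed the full Safe-anastomosis Online Educational Module (all five modules) before the date of this operation? Yes / No.* Preferably add month and year of completion. Use this status, not status at data entry, in any analysis or description by training. Naming all five modules removes the remaining doubt about scope at no extra cost. A field separating EAGLE 1 from revised training is not warranted, because the protocol does not establish that the revision followed EAGLE 1.

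The cost is one reworded item and perhaps one short field. Some records will move from Yes to No, which lowers reported uptake and may move centres between bands.

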- Anastomotic leakage identified radiologically or clinically
or
- Intraperitoneal (abdominal or pelvic) fluid collection identified radiologically, as per the Centre for Disease Control Criteria for Organ Space infection
or
- Entero-enteric fistula identified radiologically

Secondary outcome measures

- The denominator is the total for patients who had a primary anastomosis:
- Reoperation for anastomotic leak, within 30-days
- The denominator is the total for all patients:
- Reoperation for any cause, within 30-days
- Unplanned admission to critical care, within 30 days
- Readmission within 30 days.
- Post-operative length of hospital stay, up to 30-days
- Mortality within 30-days.
- Rate of ileostomy without anastomosis.
- Rate of defunctioning ileostomy with anastomosis.

Study Design

International prospective audit.

ELIGIBILITY

Hospital inclusion criteria

Any hospital or surgical unit performing elective and/or emergency colorectal surgery. There are no restrictions for hospital/unit size or case volume. Participation in EAGLE 1 is not a pre-requisite.

Participating sites will be expected to recruit all eligible patients within a consecutive 8-week period.

At hospital level, data completeness of 95% will be required to be part of this audit.

Patient inclusion criteria

All adult patients (age 18 years and above) undergoing right colectomy with or without primary anastomosis. Right colectomy is defined as ileocaecal resection or right hemicolectomy (any colonic transection with the distal resection margin proximal to the splenic flexure).

All patients undergoing right colectomy are eligible, including those who do not have an anastomosis and are defunctioned by a proximal stoma.

Procedures for any pathology, via any operative approach (open, laparoscopic, robotic or converted) are eligible.

Elective (surgery on a planned admission), expedited (within 48 hours), and emergency (surgery on an unplanned admission) procedures are eligible.

Patient exclusion criteria

Patients undergoing more than one gastrointestinal anastomosis during the same operation.

In Crohn's disease, additional upstream strictureoplasty or resection/anastomosis to treat disease or strictures at the same operation.

Simultaneous right colectomy and hyperthermic intraperitoneal chemotherapy (HIPEC) and/or cytoreductive surgery.

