The audit is designed so that normal patient follow-up pathways can be utilised to obtain outcomes' data. No additional visits or changes to normal follow-up should be made. However, local investigators should be proactive in identifying post-operative events (or lack thereof), within the limits of the follow-up period (30 post-operative day). These may include reviewing the patient notes (paper and electronic) during admission and before discharge to register in-hospital complications, reviewing hospital systems to check for re-attendances or re-admissions, and reviewing post-operative radiology reports, as well as the notes from the in-person outpatient review which we anticipate will occur within the 30 days post-operation in most circumstances.

Data completion and organisation

As EAGLE 2 is an audit, no changes to the normal patient pathway need to be instigated for it to be run.

Data Management

Information will be collected at the following times:

- Short-term follow-up: At baseline (surgeon level)
- At 30 days after the operation (surgeon level). The day of operation will be considered day zero

Data will be entered directly onto the secure electronic REDCap database by study collaborators at the participating hospital sites using pseudonymised data.

Site study collaborators will be provided with a paper copy of the eCRF to facilitate data collection. If this is used, they should then transfer data from the paper CRF into the online database (<https://www.bistc.redcap.bham.ac.uk>). Data management staff will check all incoming data CRFs for completeness, data consistency and compliance with the protocol. If discrepancies or missing data are identified, the data management staff will raise queries with the research team at the participating hospital via the study database.

Source Data

Source data within the EAGLE 2 audit will be kept as part of the participants' medical notes generated and maintained at site. As all data collected and analysed within the EAGLE 2 audit are routinely collected, source data will only be within the medical notes.

Data handling and record keeping

The security of the Study Database System is governed by the policies of the University of Birmingham. The study database will be hosted on the REDCap system managed and maintained by BiCOPS.

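### The critical-care item reads as single choice with options that overlap over 30 days and no rule of precedence, so unplanned admissions may be coded inconsistently and under-counted.

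*Protocol*

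**What the plan says.** Under Secondary outcome measures, the protocol lists "Unplanned admission to critical care, within 30 days". It sits in the group headed "The denominator is the total for all patients", so patients with and without an anastomosis both count.

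In the Case Report Form (Appendix 1, post-operative data), one item records post-operative critical-care admission, with the answers "None / Planned from theatre / Unplanned from theatre / Unplanned from ward". No other field on the form records critical-care admission.

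Two other features of the form bear on how the item will be read. The intra-operative complications item is the only one marked for multiple answers; its list ends "Hemodynamic instability / Vasopressor requirement (select all that apply". And neighbouring post-operative items carry their window in the label, for example "Re-operation within 30 days", whereas the critical-care item does not.

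On timing, the Data Management section has follow-up information collected "At 30 days after the operation (surgeon level). The day of operation will be considered day zero".

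**The concern.** The outcome asks a yes/no question: did this patient have any unplanned critical-care admission in 30 days? The form asks a different one: which of four categories describes the patient's critical-care admission? The two agree when a patient has at most one admission. They can part when a patient has a planned admission from theatre and a later unplanned one, because two of the four answers are then true and the form does not say which to give.

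If the planned answer is given, the patient is counted as having no unplanned admission. The record is complete and internally consistent, so neither the 95% completeness requirement nor the central consistency checks need raise a query. An analysis plan could not repair it either, because the second admission was never collected. At stake are the accuracy of one secondary outcome and its comparability between sites, including in the unit-level breakdowns that the Publication policy section offers for benchmarking.

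**Working it through.** **Does the item fit the outcome?** The protocol states no rate, sample size or power for this outcome, so there is no figure to reproduce. The main check is a comparison of the form's options with the outcome definition.

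| Course over 30 days | True answer(s) on the form | Counted in the outcome? |
|---|---|---|
| No critical care | None | No, correctly |
| Planned from theatre only | Planned from theatre | No, correctly |
| Unplanned only, from theatre or ward | The matching unplanned option | Yes, correctly |
| Planned from theatre, later unplanned from ward | Two options are true | Depends on which is entered |
| Unplanned only, directly on readmission | No option fits | Depends on how the site improvises |

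The last two rows are the gap. In the fourth, entering the planned option can only lower the count.

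**Is it single choice?** The form does not say so. The inference rests on contrast: multiple answers are invited on one item and not on this one. It is the natural reading of the printed form.

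**How large could the loss be?** All inputs here are assumptions; none is in the documents.

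- p, share of patients with a planned admission: 10% to 30%.
- r, share of those with a later unplanned admission: 2% to 10%.
- m, share of double-admission patients coded as planned: 0%, 50% or 100%.
- u, unplanned rate in patients without a planned admission: 3%.

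Patients lost = p × r × m. True unplanned rate = u × (1 − p) + p × r. Relative under-count = lost ÷ true.

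Worked example, p = 30%, r = 10%, m = 100%: lost = 0.30 × 0.10 × 1 = 0.030, or 30 per 1,000; true = 0.03 × 0.70 + 0.30 × 0.10 = 0.051, or 51 per 1,000; relative under-count = 30 ÷ 51 = 58.8%.

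| p | r | True per 1,000 | Lost, m = 0 | Lost, m = 50% | Lost, m = 100% |
|---|---|---|---|---|---|
| 10% | 2% | 29 | 0 | 1 (3.4%) | 2 (6.9%) |
| 10% | 10% | 37 | 0 | 5 (13.5%) | 10 (27.0%) |
| 30% | 2% | 27 | 0 | 3 (11.1%) | 6 (22.2%) |
| 30% | 10% | 51 | 0 | 15 (29.4%) | 30 (58.8%) |

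The range runs from nothing to more than half of events, and the coding share m matters as much as the clinical rates. The calculation covers only the planned-then-unplanned course; direct admission on readmission is not included.

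**The case against.** The strongest reply is that the event can be recorded. The unplanned-from-ward option is available, and outcomes are collected at 30 days, when the recorder can know of both admissions. A patient so coded counts correctly, and all that is lost is the planned admission, which is not an outcome. This stands. A reader might infer that a second, unplanned admission cannot be entered at all, or that the outcome is bound to be under-counted; the documents support neither. What cannot be entered, if the field is single choice, is both admissions together.

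The reply also notes that single choice is inferred, that the REDCap build and any completion guidance are not shown, and that a precedence rule may sit there. That is fair, and it limits confidence. But sites are given a paper copy of the form, so its printed wording will guide coding, and it carries no rule.

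The missing window on the label is a weak point by itself. The outcome definition and the follow-up period both fix 30 days, and the leak item has no window on its label either. It matters only because it makes it easier to read the item as asking where the patient went straight after surgery.

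Two further inferences should be resisted. That the loss falls on the highest-risk patients is plausible, but the documents give no data on it. That it distorts comparisons between income groups does not follow from the plan: the pre-planned subgroup analyses, including income group, are of the primary outcome only.

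**Conclusion.** The point holds as a data-capture flaw in one secondary outcome. The options overlap over 30 days, the item reads as single choice, no rule of precedence is printed, direct admission on readmission has no option, and no other field recovers a second admission. Sites may therefore code the same course differently, and in planned-then-unplanned patients any error lowers the count.

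The size cannot be determined from the documents. It is zero if sites consistently choose the unplanned option. Under the assumed rates, with every double-admission patient coded as planned, it is 2 to 30 patients per 1,000, or about 7% to 59% of events. Those figures illustrate the range and do not estimate it. The conclusion also rests on the field being built as single choice. The primary outcome, its denominator and its model are untouched, so this is an inexpensive improvement and not a threat to the audit's main result.

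**What to change.** Replace the item with two fields:

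- *Planned critical-care admission from theatre*: No / Yes.
- *Any unplanned critical-care admission within 30 days*: No / from theatre / from ward / on readmission.

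Derive the secondary outcome from the second field alone. This removes the loss from planned-then-unplanned patients and gives direct admission on readmission a place. If the single item must be kept, print on the form that any unplanned admission within 30 days takes precedence over a planned one; this settles the count but leaves readmission without its own option.

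The cost is one extra REDCap field and the matching line on the paper form, using information already in the medical notes. It is best done before data collection starts, since correcting it afterwards would mean going back to the notes at the sites.
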